2.2 Secondary Objectives (or Aim)

The secondary objectives are to:

- Determine if a text messaging intervention using MyDiaText will improve diabetes self-management skills as measured by the Self-Care Inventory (SCI) in children 12 to 18 years.
- Analyze the response rate to educational text messages when a reward paradigm, in which children are intermittently rewarded for engaging in the application for multiple days in a row, is administered.

3 INVESTIGATIONAL PLAN

3.1 General Schema of Study Design

3.1.1 Focus Groups

Up to 5 focus groups of 10 adolescents with type 1 diabetes will be carried out to develop the text messaging intervention. Text messages previously developed for the feasibility study will be used for this intervention. These text messages will be presented to the focus group subjects to determine whether changes need to be made. The focus groups subjects will also have input on other details of the intervention such as frequency and timing of the text messages. Subjects for these focus groups will be recruited from the CHOP Endocrinology and Diabetes outpatient clinic. Focus groups will last about one hour. They will be held in a private location at a time that is convenient to the subjects. Focus groups will be digitally recorded and transcribed. Subjects of these focus groups will be excluded from participation in the intervention phase.

3.1.2 Inclusion Criteria for Focus Groups

- 1) Males or females age 12 to 18 years.
- 2) Have a diagnosis of T1DM for more than 1 year.
- 3) Own a personal mobile device.
- 4) Parental/guardian permission (informed consent) and, if appropriate, child assent.

3.1.3 Exclusion Criteria for Focus Groups

- 1) Subject is non-English speaking.
- 2) Subject has a significant cognitive disability.
- 3) Subject does not have insurance approval for point-of-care A1C measurement

3. 2 General Schema for Intervention Study

3.2.1 Screening Phase

Potential subjects will be recruited from the CHOP Endocrinology and Diabetes outpatient clinic. Clinic schedules will be reviewed for determination of potential subjects as per the inclusion criteria above. Some subjects will be pre-screened for interest only, without eliciting PHHI, by telephone prior to their clinic visit. Subjects will be approached during their clinic visit and informed about the current study. If the subject agrees to participate, informed consent (from caregiver if subject is < 18 y/o and from subject if he/she is >18 y/o) as well as assent if subject is < 18 y/o will be obtained. HbA1c and diabetes treatment plan will be collected from the medical record.

3.2.2 Phase 1

This phase will start enrollment. Subjects will be registered into the MyDiaText website by research staff. At registration, MyDiaText will randomize half of the subjects to the intervention group and the other half to the control group. At this time, SCI will be administered via a text message link to the MyDiaText website; this will serve also to ensure the phone number for the patient was entered correctly and that account is active for log-in. All subjects will get \$5 upon completion of baseline self-care inventory. All subjects, control and intervention, will create a profile in the MyDiaText system. This profile will consist of his/her name, birthday, gender, ethnicity, phone number, and email. All subjects will be following their diabetes care plan as dictated by their primary diabetes provider. The subjects in the intervention group will start receiving the text messaging intervention as described in the intervention section (section 7). Subjects in the intervention group will be instructed to respond to each text as a proxy for having read it. Previously, a point system reflected scoring on quizzes and educational activities. To update the text messages based on current technology, all quizzes have been transitioned into text messages. To address gaps in research, a specific reward paradigm was created based on the concept of “streaks,” or reward for consecutive days of engagement in the application. Those with the longest “streak” will be placed in a drawing for an extra cash prize of \$10 every two weeks.

3.2.3 Phase 2

This phase will start at their next visit with their diabetes provider, which usually occurs after 3 months +/- 1 month. During this phase, control group will continue to not receive text messages, and intervention group will continue to receive text messages. HbA1c and diabetes treatment plan will be collected from the medical record. SCI will be completed at this time. All subjects will get \$10 for completing the second SCI. Invitation to fill out second SCI will be administered via text message. If second SCI is not filled out 7 days after this invitation, a reminder text message will be sent. If not filled out 7 days after reminder text message, a second reminder text message will be sent. No further reminders for that SCI will be sent.

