Study Phases	(1) Pre-screening : focus groups to determine details of the intervention
Screening	(2) Screening : screening for eligibility and obtaining consent, review medical record for HbA1C, obtain baseline Self-Care Inventory score
Study Treatment	(3) Intervention : review medical record for HbA1C, obtain Self-Care Inventory score
Follow-Up	(4) Follow-up : review medical record for HbA1C, obtain Self-Care Inventory score, complete satisfaction survey
Efficacy Evaluations	The primary efficacy endpoint will have two parts: the change in HbA1c between control and intervention groups between visit 1, 2 and 3.
Safety Evaluations	Adverse events are not anticipated in this study.
Statistical And Analytic Plan	Descriptive data analysis will include estimating means and standard deviations for continuous variables and counts and proportions of categorical variables for all aims. Two sample t-tests will be used to evaluate changes in HbA1c and SCI scores between the control and intervention groups and paired t-tests (or nonparametric methods if data is not normally distributed) will be used to compares the above changes within each group.
Data and Safety Monitoring Plan	The PI will monitor study progress, ensure the accuracy and security of the data, and ensure subject safety.

TABLE 1: SCHEDULE OF STUDY PROCEDURES

Study Phase	Screening	Control	Intervention	Follow-Up
Visit Number		1	2	3
Study Days		90 (+/- 30 days)	90 (+/- 30 days)	1
Informed Consent/Assent	X			
Review Inclusion/Exclusion Criteria	X			
Randomization	X			
Intake Questionnaire		X		
Height and Weight		X	X	X
HbA1c		X	X	X
SCI Questionnaire		X	X	X
Exit Questionnaire (Subjective Assessment of Intervention)				X

FIGURE 1: STUDY DIAGRAM

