3.3 Allocation to Treatment Groups and Blinding

Half of the subjects will be randomized to the intervention and the other half will serve as controls. MyDiaText will randomly assign patients to treatment or control upon registration. Given the nature of the intervention, subjects will not be blinded. All study personnel and diabetes providers will not be blinded to current subject phase during the study, since unblinding should not result in bias in this study and it would be difficult to ensure that subjects do not tell their providers whether or not they are receiving text messages.

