4.2 Screening Visit (Visit 1)

Screening will take place just prior to Phase 1. It will consist of explaining the study and screening for eligibility. Subjects that qualify and are interested will move on to Phase 1

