4.3 Study Treatment Phase

4.3.1 Visit 1

- Informed Consent and/or Subject Assent
 - Medical Record Review
 - Lab: hemoglobin A1c
-

- Registration on MyDiaText website by study staff
- SCI questionnaire

4.3.2 Visit 2

- Medical Record Review
- Lab: hemoglobin A1c
- SCI questionnaire

4.3.3 Visit 3

- Medical Record Review
- Lab: hemoglobin A1c
- SCI questionnaire
- Exit questionnaire

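### The self-reported baseline SCI is sent at the same step as randomisation in an unblinded trial, and nothing holds back the arm or the first text until it is answered

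*Combined protocol and SAP*

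**What the plan says.** Two sections tie allocation to registration. Section 3.2.2 (Phase 1) says "At registration, MyDiaText will randomize half of the subjects to the intervention group and the other half to the control group", and section 3.3 says "MyDiaText will randomly assign patients to treatment or control upon registration". Directly after the randomisation sentence, section 3.2.2 adds "At this time, SCI will be administered via a text message link to the MyDiaText website". It explains that the link also checks the phone number and that the account works for log-in. The same section then describes the profile, the start of texts in the intervention group, and the instruction to that group to reply to each text. None of these steps is made conditional on a completed SCI.

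On blinding, section 3.3 says "Given the nature of the intervention, subjects will not be blinded", and sections 3.3 and 9.1.2 say the same of study personnel and diabetes providers.

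Other places touch on timing without fixing it:
- The synopsis lists among the screening tasks "review medical record for HbA1C, obtain baseline Self-Care Inventory score".
- Table 1 marks randomisation under Screening and the SCI under Visits 1, 2 and 3.
- Section 4.2 says of screening: "It will consist of explaining the study and screening for eligibility".
- Section 4.3.1 lists, among the Visit 1 items, "Registration on MyDiaText website by study staff", followed by the SCI.
- Section 5.3.1 expects the SCI to be done at each study visit.
- Sections 3.2.3 and 3.2.4 give 7-day reminders for the second and third SCI. The baseline SCI has no reminders and no stated completion window.

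**The concern.** The SCI is a self-report. A subject who knows they will get the texts, or knows they will not, may rate their own care differently on the first day. The usual protection is to collect the baseline before allocation, or at least before anyone discloses it. Here the link is sent through the registered account, and registration triggers randomisation. Read literally, the allocation already sits in the system when the subject opens the questionnaire.

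The baseline enters the endpoint directly, because sections 6.1 and 6.3.2 analyse the change in SCI from Visit 1 to Visit 2. A shift of equal size at both visits would cancel. The plan cannot count on that, because by Visit 2 one arm has had about 90 days of texts and at Visit 1 neither has had any. Section 3.3 argues that leaving personnel and providers unblinded should not cause bias, but it does not address a subject's own answers at baseline.

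**Working it through.** **Step 1: what order do the documents fix?**

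| Place | What it establishes |
|---|---|
| 3.2.2, 3.3 | Randomisation happens at registration |
| 3.2.2 | Baseline SCI is sent at that same step, through the registered account |
| 3.3, 9.1.2 | Subjects, personnel and providers are unblinded |
| 3.4.1, heading of 4.2 | Screening falls on the first day of Phase 1 and is labelled Visit 1 |
| Table 1, synopsis, 4.3.1 | Items grouped by phase or visit, with no stated order within the day |

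Because screening and Visit 1 are the same day, the Table 1 columns and the 4.3.1 list do not establish a sequence, and neither does the synopsis. The point rests on 3.2.2 and 3.3.

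**Step 2: is there a safeguard?** None appears in the sections on registration, randomisation, SCI timing, blinding or the start of texts. No section says when subjects are told their arm.

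**Step 3: what could it do to the test?** The documents give no SCI SD, visit-to-visit correlation, size of shift or share of subjects who would know their arm. What follows is illustration on assumed values.

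Inputs from the documents: two-sided alpha 0.05 (6.3.2), and 82 or 100 per arm, from 164/2 and 200/2 (6.4; the 164 comes from the HbA1c calculation). The test is the two-sample comparison named in the synopsis; section 6.3.2 names paired t-tests for the SCI. Assumed: no true effect, no loss, and SD of change set to 1.

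Net shift d = baseline shift × (1 − share recurring at Visit 2). The noncentrality is d / √(2/n), with 2n − 2 degrees of freedom. For d = 0.2 this is 0.2/√(2/82) = 1.281 and 0.2/√(2/100) = 1.414.

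| Net shift d (SD of change) | False-positive rate, 82 per arm | 100 per arm |
|---|---|---|
| 0 | 0.050 | 0.050 |
| 0.05 | 0.062 | 0.064 |
| 0.1 | 0.098 | 0.108 |
| 0.2 | 0.247 | 0.291 |

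A baseline shift of 0.2 therefore gives 25–29% if none of it recurs at Visit 2, 10–11% if half recurs (d = 0.1), and 5% if all recurs (d = 0).

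**Step 4: would baseline adjustment remove it?** With visit-to-visit correlation ρ, a baseline-only shift b leaves a bias of size ρb. The SCI SD is 1/√(2(1 − ρ)), and the noncentrality is ρb / [SD × √(1 − ρ²) × √(2/n)]. For b = 0.2:
- ρ = 0.5 (SD = 1): noncentrality 0.739 and 0.816, rejection about 11% and 13%.
- ρ = 0.7 (SD = 1.291): noncentrality 0.972 and 1.074, rejection about 16% and 19%.

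Adjustment reduces the bias and does not remove it.

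**The case against.** The strongest reply is that the harm needs an event the documents never describe. Staff do the registration, software does the assignment, and nothing says the arm is announced then. Section 3.3 attributes the lack of blinding to the nature of the intervention, which may mean only that subjects find out when texts arrive. The narrative in 3.2.2 mentions the SCI link before the texts, and 5.3.1 expects completion at the visit, so intervention texts arriving before a baseline SCI done as planned are unlikely.

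Most of this stands. A reader might infer that the baseline SCI is answered after subjects know their arm; the documents do not say so. A reader might also take Table 1 or the 4.3.1 list as proof that the SCI follows randomisation; they are same-day groupings and prove no order. The assumed shifts are no better supported than a shift of zero.

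What does not fall is the gap itself. Completion at the visit is not completion before disclosure when randomisation happens at that visit. The instruction to reply to texts would reveal the arm, and nothing delays it until the SCI is in.

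It can also be said that open-label self-report at Visit 2 is exposed in any case. That is true, but it is a separate source of bias, and the exposure at baseline is avoidable.

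**Conclusion.** The point holds as an unprotected sequence: randomisation and the self-reported baseline SCI share one step, nobody is blinded, and no rule keeps the arm or the first text back. It is worth correcting before enrolment, because an affected baseline cannot be collected again.

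The size and direction of any bias are unknown. The figures of about 6% to 29% depend wholly on assumed net shifts of 0.05 to 0.2 SD of change, no true effect and a two-sample test. They should not be read as the trial's expected error rate. The weight of the point also depends on an unresolved conflict: the SCI change is primary in 6.1 and 6.3.2 and secondary to HbA1c in the abstract and synopsis. My confidence is medium.

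**What to change.** State one order within Visit 1 in 3.2.2, 3.3, 4.3.1, Table 1 and the synopsis:
1. Create the account.
2. Send the SCI link, which keeps the phone and log-in check.
3. Have the subject complete the baseline SCI at the visit.
4. Have MyDiaText randomise and release the arm.

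If the software cannot separate registration from randomisation, keep the arm undisclosed to subject and staff until the SCI is submitted or Visit 1 ends, whichever is first, and then start the intervention as allocated. The end-of-visit limit matters. Section 6.3.2 defines the analysis set by randomisation and a Visit 2 HbA1c. If texts waited indefinitely for an SCI, a randomised subject who never completed it would go untreated yet stay in that set, diluting the HbA1c comparison.

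Under either option, record whether the SCI was completed before disclosure.

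The cost is a change to the registration sequence (the documents do not say how much work that is) and a few minutes at Visit 1. Under the first option, a subject who does not complete the baseline SCI is not randomised, and the protocol should say so. The change protects the baseline only; it does not remove open-label self-report bias at Visit 2.

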3.2.4 Follow-up Phase

This phase will start and end at their next visit with their diabetes provider (second from randomization). This phase will only entail data collection on that day. HbA1c and diabetes treatment plan will be collected from the medical record. SCI will be completed at this time as well as a questionnaire assessing the intervention. Invitation to fill out third SCI and intervention assessment will be administered via text message. If third SCI and intervention assessment are not filled out 7 days after this invitation, a reminder text message will be sent. If not filled out 7 days after reminder text message, a second reminder text message will be sent. No further reminders for survey completion will be sent after this point. All subjects will get \$15 for completing the third SCI and intervention assessment. This phase will conclude the study.

3.3 Allocation to Treatment Groups and Blinding

Half of the subjects will be randomized to the intervention and the other half will serve as controls. MyDiaText will randomly assign patients to treatment or control upon registration. Given the nature of the intervention, subjects will not be blinded. All study personnel and diabetes providers will not be blinded to current subject phase during the study, since unblinding should not result in bias in this study and it would be difficult to ensure that subjects do not tell their providers whether or not they are receiving text messages.

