The main outcome measure will be change HbA1c. The secondary outcome measure will be change in scores of the Self-Care Inventory questionnaire.

PROTOCOL SYNOPSIS

[figure not shown]
Study Title	MyDiaText: Texting the Way to Better Diabetes Control
Funder	NIH T32 Grant-Pediatric Endocrinology Division of CHOP
Clinical Phase	intervention
Study Rationale	Optimal control of type 1 diabetes may prevent, or at least decrease the risk of, diabetes complications. Adolescents with diabetes often have difficulty adhering to a diabetes management plan such a monitoring of blood glucose levels, administering insulin, and eating healthy. There is a need for an intervention that will resonate with youth and support adolescents with type 1 diabetes to improve their self-management practices in order to improve their glycemic control and prevent or reduce the risk of short- and long-term complications.
Study Objective(s)	
Primary
 
 To develop a text messaging intervention using MyDiaText and to determine whether such an intervention will decrease HbA1c in children 12 to 18 years 
Secondary
 
 To determine if a text messaging intervention using MyDiaText will improve diabetes self-management skills as measured by the Self-Care Inventory (SCI) in children 12 to 18 years
Test Article(s)	The intervention will consist of daily text messages sent to the subject's personal mobile device. Previously developed text messages and quiz questions based on the ADA behavior goals will be used for this intervention.
Study Design	Randomized trial
Subject Population key criteria for Inclusion and Exclusion:	
Inclusion Criteria
 
 Subjects age 12 to 18 year of age. Have a diagnosis of T1DM for more than 1 year. HbA1c \geq 8% but $<$ 14%. Have been seen in the diabetes clinic in the last 6 months. Own a personal mobile device with unlimited text messaging plan. Parental/guardian permission (informed consent) and, if appropriate, child assent. 
Exclusion Criteria
 
 Non-English speaking. Significant cognitive disability or major organ illness. Hemolytic anemia.

4. Ongoing oral steroid use	
Number Of Subjects	200 subjects will be recruited from Diabetes Clinics affiliated with the Children’s Hospital of Philadelphia
Study Duration	Each subject’s participation will last for approximately 180 days

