4.5 Subject Completion/Withdrawal

Subjects may withdraw from the study at any time without prejudice to their care. They may also be discontinued from the study at the discretion of the Investigator for lack of adherence to study treatment or visit schedules. The Investigator may also withdraw subjects who violate the study plan, or to protect the subject for reasons of safety or for administrative reasons. It will be documented whether or not each subject completes the clinical study.

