6 STATISTICAL CONSIDERATIONS

6.1 Primary Endpoint

The primary endpoint will be the change in SCI score between Visit 1 and Visit 2 in control group as compared to intervention group

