6.3.2 Efficacy Analysis

The primary analysis will include all subjects randomized at Visit 1 who have gotten HbA1c measurements at visit 2. The primary efficacy endpoint will be the change in SCI Score.

The first analysis will be change in SCI score from visit 1 to visit 2 comparing treatment and control groups. For this analysis we will use paired t-tests to test the null hypothesis of no difference in change in SCI scores at the two-sided $\alpha = 0.05$ level.

The secondary analysis will be the change in HbA1c between the intervention and control group from visit 1 to visit 2. For this analysis we will use two sample t-test to test the null hypothesis of no difference in the change in HbA1c at the two-sided $\alpha = 0.05$ level.

An additional secondary analysis will be the durability of the text messaging intervention from visit 2 to 3. SCI score and HbA1C will continue to be tracked to compare visit 1 to visit 3 and visit 2 to visit 3 at study conclusions.

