9.1.3 Unblinding

No unblinding protocol needs to be established since no one is blinded in this study.

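### Section 3.3 says unblinding should not cause bias, but the primary endpoint in 6.1 and 6.3.2 is a questionnaire answered by unblinded subjects, and intervention subjects alone can be removed for not following study treatment

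*Combined protocol and SAP*

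**What the plan says.** Section 3.3 gives separate reasons for the lack of blinding. For subjects: "Given the nature of the intervention, subjects will not be blinded". For study personnel and diabetes providers there are two: "since unblinding should not result in bias in this study", and the difficulty of stopping subjects from telling their providers whether they get texts. Section 9.1.3 confirms the result: "No unblinding protocol needs to be established since no one is blinded in this study".

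The statistical sections make the SCI primary. Section 6.1: "The primary endpoint will be the change in SCI score between Visit 1 and Visit 2", compared between arms. Section 6.3.2: "The primary efficacy endpoint will be the change in SCI Score". Under 3.2.2 and 3.2.3 subjects reach the SCI by text message, through the MyDiaText system that also delivers the intervention.

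Other parts of the document point to HbA1c. The abstract: "The main outcome measure will be change HbA1c". The synopsis defines the primary efficacy endpoint as "the change in HbA1c between control and intervention groups between visit 1, 2 and 3". Section 2.1 builds the primary objective on HbA1c, and 6.4 sizes the trial on it.

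Section 4.5 allows the investigator to discontinue subjects "for lack of adherence to study treatment or visit schedules". Section 6.3.2 limits the primary analysis to randomised subjects who have a Visit 2 HbA1c.

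**The concern.** A statement that knowledge of allocation should not bias the study needs an outcome, and an analysis population, that such knowledge cannot easily move. Sections 6.1, 6.3.2 and 4.5 provide neither.

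First, the outcome. Controls receive no intervention texts, so by Visit 2 every subject knows the arm. Intervention subjects have been texted about diabetes behaviour goals, asked to answer each text, and offered prizes for unbroken runs of replies. They are then asked, through the same system, to rate their own self-care. Some may report better self-care without practising it.

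Second, the population. Controls have no study treatment to adhere to, so discontinuation on that ground can occur only in the intervention arm, at the discretion of investigators who know the arm. The subjects removed would be the poorly engaged ones. Any of them without a Visit 2 HbA1c also leave the primary analysis.

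At stake is whether a significant SCI difference could be read as efficacy. Nothing in the plan acknowledges reporting bias, provides a control for attention, or limits what an SCI result may support.

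**Working it through.** **1. The no-bias statement against the design**

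| Route for bias | Where it arises | What the plan does about it |
|---|---|---|
| Subjects rate their own self-care knowing their arm | 3.3, 3.2.2, 3.2.3, 6.1, 6.3.2 | Nothing stated |
| Texts, prizes and questionnaire come through one system; texts and prizes go to one arm only | 3.2.2, 4.3.4, 9.7.1 | Nothing stated |
| Removal for non-adherence to study treatment | 4.5 | 4.5.1 gives subjects who withdraw the Visit 3 procedures |
| Analysis requires a Visit 2 HbA1c | 6.3.2 | No rule for discontinued subjects |
| Providers who know the arm direct the care plan | 3.3, 3.2.2 | Treatment plan is collected at visits; no analysis of it is specified |

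**2. The plan's own figure.** Section 6.4 gives 164 subjects for a difference of 1 in HbA1c percentage points, SD 2.26, 5% level, 80% power. Taking the test as two-sided with 1:1 allocation:

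- Normal approximation: n per arm = 2(1.960 + 0.842)² × 2.26² / 1² ≈ 80.2, so 81 per arm and 162 in total.
- Two-sample t-test: 81.15, so 82 per arm and 164 in total. This matches exactly.

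The 164 is therefore a parallel-group size for HbA1c, although 6.4 calls the study a cross-over. It says nothing about power or error for the SCI. With the same inputs, HbA1c power by the normal approximation is about 81% at 82 per arm and 88% at 100 per arm.

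**3. Illustration of reporting bias on the SCI.** The documents give no SCI standard deviation, expected change or expected reporting shift. Let b be an assumed shift in mean reported SCI change in the intervention arm, in SD units, with no true effect. For a two-sided 5% two-sample test with n per arm, the test statistic is centred at δ = b√(n/2) and

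P(p<0.05) ≈ 1 − Φ(1.960 − δ) + Φ(−1.960 − δ).

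Example with b = 0.2, n = 100: δ = 0.2 × √50 = 1.414, so P ≈ 1 − Φ(0.546) + Φ(−3.374) ≈ 0.293. The t-test version gives 0.291. Results from the t-test:

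| Assumed shift b | 82 per arm | 100 per arm |
|---|---|---|
| 0 | 5% | 5% |
| 0.1 SD | 10% | 11% |
| 0.2 SD | 25% | 29% |
| 0.3 SD | 48% | 56% |
| 0.4 SD | 72% | 80% |

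The normal approximation differs by at most one percentage point. The two-sample test is the one in the synopsis; 6.3.2 names paired t-tests for the SCI comparison between arms, and that also needs reconciling.

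**The case against.** Five points can fairly be made for the plan.

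- **Subjects cannot be blinded to receiving texts.** This stands in full. The open design is not a fault.
- **The no-bias clause is about personnel and providers, and is worded as an expectation.** Also true. A reader might infer that the plan claims bias is impossible, or relies on this clause to justify unblinded subjects. It does neither. But the clause speaks of the study without qualification, and it is unsupported even for personnel, given the discretion in 4.5 and the analysis population in 6.3.2.
- **The clause was not used to choose the SCI.** A reader might infer that the plan lets the SCI alone decide the result because it believes unblinding is harmless. The documents show no such link: 3.3 does not mention the SCI, 6.1 and 6.3.2 do not mention blinding, and the abstract, synopsis, 2.1 and 6.4 all point to HbA1c. The endpoint conflict is a defect in its own right; here it matters because the SCI is the endpoint more exposed to reporting bias.
- **Some protection exists.** Section 4.5.1 gives subjects who withdraw the Visit 3 procedures, which include HbA1c, and the visit-schedule ground in 4.5 applies to both arms. This stands in part. Section 4.5.1 does not clearly cover discontinuation by the investigator, does not secure a Visit 2 value, and does not say how these subjects are analysed.
- **The percentages are a power curve with bias in place of effect.** Correct. They show how sensitive the test is to a shift. They are not evidence that a shift of any given size, or in that direction, will occur.

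**Conclusion.** The concern holds in this limited form: the no-bias statement in 3.3 is not supported by the design, and the plan mitigates neither reporting bias in the SCI nor the one-sided discontinuation ground. The change should be made.

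The size of any bias cannot be computed from the documents. The table is conditional on an assumed shift in favour of the intervention, no true effect and a two-sample test. It shows that even 0.1 SD would roughly double the nominal 5% error, and 0.2 SD would raise it five- to six-fold. The effect of selective discontinuation is not quantified, because the documents give no expected numbers.

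A reader might infer that moving to HbA1c removes bias altogether. It does not: unblinded providers could manage the arms differently. HbA1c is much less open to reporting bias because it is a laboratory value.

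**What to change.** 1. **Section 3.3.** Delete the clause saying unblinding should not result in bias. State instead that the SCI is self-reported by unblinded subjects and open to reporting bias. The practical reason for unblinded providers can stay.
2. **Sections 6.1, 6.2 and 6.3.2.** Reconcile these with the abstract, synopsis, 2.1 and 6.4 by making the between-arm change in HbA1c from Visit 1 to Visit 2 the primary endpoint and the basis of any efficacy claim, with the SCI supportive. The change must be written into the statistical sections; putting it only in 3.3 would create a new contradiction.
3. **Sections 4.5 and 6.3.2.** State that subjects discontinued for non-adherence stay in their randomised arm for analysis, and that their routine-care Visit 2 HbA1c is still taken from the medical record unless they withdraw consent.

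The cost is protocol wording. Section 5.3.1 says HbA1c is already checked every 3 months as part of care, and the sample size already rests on it, so no new visits or subjects follow from the change. The downside is that a positive SCI result alone would no longer count as success. Masking arm codes in the analysis or withholding allocation from providers would add little: neither touches self-reporting, and subjects may tell their providers anyway.
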